### **Data analysis and sample size calculations**

We have conducted a Bayesian power analysis for this study comparing combination therapy with nifedipine and indomethacin versus single agent therapy with nifedipine alone for treatment of acute preterm labor. Our primary outcome is the percentage of women that remain pregnant at >48 hours.

#### **Design prior distributions:**

Single agent outcome rate: 77% (95% CI: 68%-85%)

Combination outcome rate: 95% (95% CI: 74%-99.9%)

Our clinically important absolute difference (combination % - single agent %) of > 10%. Pr(difference >10%)> level of certainty. Our enthusiastic prior is the same as the design prior above. Neutral prior assumes no difference between two groups, RR=1.0 with 95% CI of 0.5-1.33.

Level of Certainty	N per group	Bayesian Power	
		Enthusiastic prior	Neutral prior
67%	30	0.83	0.77
	40	0.85	0.80
	50	0.85	0.83
75%	100	0.86	0.83
	30	0.80	0.72
	50	0.83	0.79
80%	100	0.84	0.81
	30	0.77	0.68
	50	0.79	0.77
	100	0.84	0.80

For the primary outcome of % of women that remained pregnant > 48 hours, we assumed rates of 77% (95% Credible Interval: 68%-85%) in the nifedipine alone group and 95% (95% Credible Interval: 74%-99.9%) in the nifedipine-indomethacin group. We assumed an absolute risk difference (RD) of 10% between the two groups as the minimum clinically important treatment effect. We are interested in a posterior probability of 67% or more for this effect, i.e. Pr(RD>0.10) > 0.67. We conducted a simulation study to calculate the needed sample size to have 80% power to detect an RD >10% with 67% probability. We used the expected outcome rates to simulate data, and we assumed a neutral prior (meaning no a priori difference between the two groups with a RD centered at 0) for the final analysis. A sample size of n=40 per group will have 80% power of detecting a RD of 10% or more with 67% certainty.

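### Does the plan overstate its power by claiming 80% to detect a 10-point difference?

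*Combined protocol and SAP*

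**What the plan says.** All of this is in the combined protocol and SAP, under Data analysis and sample size calculations, subsection Design prior distributions.

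- Design rates: "we assumed rates of 77% (95% Credible Interval: 68%-85%) in the nifedipine alone group and 95% (95% Credible Interval: 74%-99.9%) in the nifedipine-indomethacin group".
- Role of 10 points: "We assumed an absolute risk difference (RD) of 10% between the two groups as the minimum clinically important treatment effect".
- Decision rule: "We are interested in a posterior probability of 67% or more for this effect, i.e. Pr(RD>0.10) > 0.67".
- Power target: "We conducted a simulation study to calculate the needed sample size to have 80% power to detect an RD >10% with 67% probability".
- Data generation: "We used the expected outcome rates to simulate data".
- Priors: "Our enthusiastic prior is the same as the design prior above", and "Neutral prior assumes no difference between two groups, RR=1.0 with 95% CI of 0.5-1.33". The neutral prior is the one chosen for the final analysis.
- Conclusion: "A sample size of n=40 per group will have 80% power of detecting a RD of 10% or more with 67% certainty".

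The power table has a column for each analysis prior. At 67% certainty and n = 30/40/50/100 it gives 0.83/0.85/0.85/0.86 (enthusiastic) and 0.77/0.80/0.83/0.83 (neutral). The certainty labels are displaced in the extracted text, and I read these four rows as the 67% block.

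**The concern.** Two things look wrong at first.

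First, a protocol that names a minimum important effect and then quotes power to detect it is usually understood to mean power when the truth equals that effect. Here the 10 points is the threshold the posterior must clear, while the 80% comes from rates centred 95 − 77 = 18 points apart. On the wrong reading, a result that missed the rule would look like good evidence against a 10-point benefit, although a true 10-point benefit would miss the rule at least two times in three.

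Second, the text does not state outright whether data were simulated at fixed rates of 77% and 95% or with rates drawn from the design priors. The answer changes what the 80% means. Power at fixed rates climbs towards 1 as n grows. An average over the priors levels off near the prior probability that the difference exceeds 10 points.

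**Working it through.** **Inputs from the plan.** Control 77% (68%–85%); combination 95% (74%–99.9%); neutral prior RR 1.0 (0.5–1.33); success if Pr(RD>0.10 | data) > 0.67; n = 40 per group; stated power 0.80.

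**Assumed prior shapes** (the plan gives none):
- Control: Beta(71.1, 21.2), mean 77%, interval 68%–85%.
- Combination, design: Beta(7.75, 0.41), mean 95%, 2.5% point 74%. Its upper limit is a little above the stated 99.9%.
- Neutral analysis prior: control as above and combination Beta(4.62, 1.38), which gives RR about 1.04 with 95% interval roughly 0.51–1.33.

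**Method.** For every pair (x, y) of control and combination successes, compute the posterior probability that p_T − p_C > 0.10 and set D(x, y) = 1 if it exceeds 0.67, otherwise 0.
- Fixed rates: power = Σ D(x, y) · Bin(x; n, p_C) · Bin(y; n, p_T).
- Averaged: replace each binomial with the beta-binomial from its design prior.

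**Step 1. Reproduce the 67% block (n = 30/40/50/100).**

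| Column | Stated | Averaged over design priors | Fixed 77% v 95% |
|---|---|---|---|
| Neutral | 0.77/0.80/0.83/0.83 | 0.767/0.792/0.804/0.825 | 0.755/0.833/0.878/0.956 |
| Enthusiastic | 0.83/0.85/0.85/0.86 | 0.85/0.86/0.85/0.85 | 0.93/0.95/0.95/0.98 |

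The averaged figures come within 3 points of all eight cells; the largest gap is 0.83 − 0.804 = 0.026. Fixed rates miss the neutral n = 100 cell by 0.956 − 0.83 = 0.126 and the enthusiastic column by 0.10 to 0.12. The prior probability that RD exceeds 10 points is 0.87 under these shapes, which explains why the stated figures level off at 0.83–0.86. The table is therefore an average over the design priors, and the 0.80 is sound on that reading.

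**Step 2. Chance of meeting the rule at n = 40, control 77%, by true combination rate.**

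| Combination | Neutral prior | Flat Beta(1,1) priors |
|---|---|---|
| 77% | 0.02 | 0.07 |
| 87% | 0.25 | 0.33 |
| 92% | 0.60 | 0.56 |
| 95% | 0.83 | 0.71 |

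Across a wider set of ten neutral and flat priors, the 87% row runs from 0.10 to 0.33.

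**Step 3. Does n matter when the truth equals the cut?** At 77% v 87% the neutral prior gives 0.25, 0.29 and 0.30 at n = 40, 200 and 600 per group; flat priors give 0.33, 0.32 and 0.32. The limit is 1 − 0.67 = 0.33: once the data dominate, the posterior probability of lying above the cut is close to uniform when the truth sits on the cut. More patients would not raise it beyond that.

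**The case for a change.** The case for a change is that the wording invites a wrong reading, the gap is large (about 0.25 against 0.80), and the remedy is cheap: two sentences reworded and a few extra simulation runs. The numbers in that case stand. It can be added that the averaged power depends on the prior shape. With the combination prior fitted to a median of 95% rather than a mean of 95%, averaged power at n = 40 under neutral priors comes out between 0.63 and 0.70, so stated prior parameters would help anyone re-deriving the figure.

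What does not stand is that the misreading is as natural as the intended one. The phrase on 67% certainty has no meaning except as the rule, which is given in symbols in the same paragraph. The 77% and 95% rates appear twice. The averaging is also signalled: the subsection heading calls the rates prior distributions, each carries a 95% interval that fixed rates would not need, and both the opening sentence and the table call the result Bayesian power. Only the sentence on how data were simulated points loosely the other way, and the table settles it.

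**Conclusion.** The concern does not call for a change. The 80% is the probability of meeting Pr(RD>0.10) > 0.67 averaged over design priors centred on 77% and 95%. It reproduces at 0.79 under the assumed beta shapes, and no stated figure is shown to be wrong. It is not power at a true 10-point difference, which is about 0.25 (0.10 to 0.33 across the priors tried) and cannot exceed about one in three at any n in those calculations. That low figure comes from placing the cut at the minimum important effect and is not evidence that 40 per group is too few.

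A tighter sentence, the prior parameters and success probabilities at other true rates would be welcome reporting. None would alter the sample size, the rule, the analysis or the result the sponsor obtains by following the plan as written. The conclusion rests on assumed prior shapes. The match to 0.80 depends on them, but the low success at 10 points held under every neutral or flat prior tried, and the poor fit of fixed rates to the table was found under each set of shapes used.

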**Potential Benefits**

In general, women will be a part of a study that may potentially affect how we manage preterm labor in pregnancy. As a specific benefit, half of the patients will be given nifedipine-indomethacin, a combination tocolytic regimen that could reduce preterm birth more than single agent therapy. We expect the combination tocolytic regimen to be at least as effective as each single tocolytic, with an average delay in delivery of at least 22 days as reported in

previous studies. Of course, patients may deliver prior to this time, or may have a longer pregnancy duration.

### **Known Potential Risks**

For this comparative effectiveness trial, there is little incremental risk as patients are receiving clinically accepted treatment regimens and the research aspect of this study is being randomized to one of these two treatment regimens vs. being assigned by treating physician. It is the practice of some physicians to use multiple tocolytic agents in tandem. There is a chance of additive maternal and fetal side effects with the two drugs being used together; however, many of the side effects are mild and reversible with the cessation of the medications. In previous trials using combination tocolytics, the risk of adverse side effects was not significantly amplified in the combination therapy group. It is unlikely that the side effects will be synergistic as the mechanisms of action of indomethacin and nifedipine differ significantly. Preliminary assessments of interaction on pharmacological engines such as the FDA and Epocrates show no known interactions between indomethacin and nifedipine.

#### *Nifedipine*

Nifedipine is a category C medication and is generally well tolerated. There are no associated teratogenic abnormalities in human pregnancies. The most frequently reported side effect in pregnancy is headache (7.5-31.2%) which is associated with transient hypotension caused by loading doses. Other reported adverse effects include flushing/heat sensation (5-43.7%), dizziness/lightheadedness/giddiness (6-27%), weakness (12%), nausea (11%), muscle cramps (8%), peripheral edema (7%), nervousness/mood changes (7%), palpitations/tachycardia (7%), dyspnea (6%) and nasal congestion/sore throat (6%). Nifedipine does not appear to influence fetal movement, heart or blood flow and thus does not have any direct fetal effects. In pregnancies with multiple gestations, nifedipine has been associated with increased dyspnea.

#### *Indomethacin*

Indomethacin is a category C medication. Fetal exposure to indomethacin is associated with the development of antenatal closure of the ductus arteriosus, antenatal oligohydramnios, postnatal persistent patent ductus arteriosus, necrotizing enterocolitis, intraventricular hemorrhage and postnatal renal failure as reported clinically and in studies in rodents. Many of these adverse events occur with prolonged courses of indomethacin administered for both greater than 48 hours and over 32 weeks gestation. Other potential risks include nausea/vomiting/heartburn/abdominal discomfort (3-9%) and headache (11.7%).

Although employed in clinical practice at times, combination nifedipine-indomethacin has not been studied within a randomized controlled trial. Prior studies have raised concern for combination tocolytic agents due to reported cases of pulmonary edema, myocardial infarction and cardiovascular collapse. However, these included ritodrine, magnesium and terbutaline, which as individual agents increase this pulmonary risk. Thus, these risks are minimal with our study combination regimen.

### **Breastfeeding**

Tocolysis is generally administered during the antepartum period and will not be used postpartum. Therefore, nifedipine and indomethacin should not affect breastfeeding.

### **Blood Draw with Venipuncture Blood**

Blood draws will be obtained from the maternal veins up to three times during the study. Possible side effects of obtaining blood samples are pain, bruising, bleeding or infection at the blood drawing site and rarely, nausea or a lightheaded feeling. A skilled nurse will be retrieving the maternal blood. A maximum of 2 tablespoons (20 ml) of blood will be obtained at each sampling for total maximum of 6 tablespoons (60 ml) for the duration of the study

### **Cord blood collection**

Cord blood collection after delivery of the newborn and prior to delivery of the placenta is a routine procedure at the time of delivery. Therefore, the risk to the subject is minimal. Approximately 2 tablespoons (20 ml) of cord blood will be obtained.

### **Myometrial biopsy**

The biopsy is performed at the site of the uterine incision as described in the methods. This uterine incision is closed using a continuous, locking suture to control bleeding. Therefore, the risk of bleeding is minimal since this site is sutured independent of this study.

### **Placental biopsy**

The risk of a placental biopsy is minimal since this is performed after delivery of the placenta.

### **Neonatal follow up**

Neonatal follow up in the study will not differ from the follow up of neonates whose mothers received single tocolytics. Neonates receive routine follow up by the pediatrician or neonatologist if the admitted to the neonatal intensive care unit (NICU). If neonatal exam is concerning in an infant antenatally exposed to indomethacin (hypotension, cardiac murmur that does not resolve), an echocardiogram will be obtained at that point to assess the ductus arteriosus. There are no known fetal effects of nifedipine. Enrollment in the study will not incur extra time commitment for mother or baby aside from the initial 48 hours to administer tocolytic therapy.

### **Cost and funding**

There is no additional cost for participation in the study, and thus, no funding is necessary for the study.

